1.0 What is the condition or intervention to be studied?

The condition to be studied is worsening (flare) of rheumatoid arthritis (RA) in patients who have undergone arthroplasty. RA patients undergoing arthroplasty most often have severe, erosive disease. If the rate of flare approaches the estimated 26% rate suggested in a previous study for RA patients after arthroplasty (*Johnson ACR 2011*), this could be of significance in regards to their long term arthroplasty and disease outcomes. Patients who flare may not be able to participate in the post-operative rehabilitation thought necessary for optimal arthroplasty outcomes, and it may be difficult for patients who flare after

*Please click
Here for
example.*

discontinuing immunosuppressant medications for surgery to regain remission or low disease activity. Detailed clinical data collected longitudinally from RA patients with severe erosive disease undergoing arthroplasty in conjunction with further characterization of the molecular profile of blood and operative tissue could provide valuable information to inform best practices for this patient group.

2.0 What is/are the research question(s)/specific aim(s)? Pose very specific questions that can be addressed within the proposed design of the study. Prioritize them in order of importance.

1. To determine the rate of post-operative RA flare within 6 weeks of surgery, defined as
 - a. Worsening of disease activity, defined as an increase in the DAS-28 by 1.2 or by 0.6 if the DAS28 was ≥ 3.2 , OR
 - b. Patient reported worsening, defined as noting they are worse or much worse on the question rating their RA since pre-surgery
 - c. AND one of:
 - i. patient wants/needs retreatment of DMARDs and/or biologics and/or prednisone increase (or Medrol dose pack or equivalent or intra-articular corticosteroid injection)
 - ii. increase in MD global of 2/10
 - iii. increase in patient global of 2/10 (on the OMERACT Preliminary Flare Questions [PFQ])
 - iv. flare severity score of ≥ 10
2. To evaluate the responsiveness of the OMERACT PFQ in patients who flare, as defined as a worsening of DAS-28 by 1.2 or by 0.6 if the DAS28 was ≥ 3.2 OR by patient reported worsening.
3. To determine predictors of post-operative flare within 6 weeks of surgery such as baseline disease activity measures and biomarkers, including molecules in the Rho associated kinase (ROCK) pathway, which are measures of immune system activation

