3.0 What is/are the hypothesis(es)?

1. 26% of RA patients will flare after TJR, defined as
 - a. Post op increases in DAS28 > 1.2 if baselines < 3.2 or > 0.6 if baseline ≥ 3.2 OR
 - b. Are worse or much worse on question rating their RA since pre-surgery AND
 - c. Have at least one of
 - i. Want / need treatment
 - ii. An increase in MD Global of 2/10
 - iii. An increase in Patient Global of 2/10 (according to the definitions noted above)
2. The OMERACT preliminary flare questions (PFQs) will detect patients who flare as defined above.
3. RA patients who flare after TJR have worse baseline pre-operative disease activity (DAS >3.2), worse baseline function (HOOS, KOOS, HAQ, elbow/shoulder surveys) and more likely will have had a history of withdrawing a biological therapy compared to patients who do not flare.
4. RA patients who flare post op will not meet their physical therapy milestones and will have worse HOOS, KOOS, elbow, or shoulder pain and function outcomes 1 year after arthroplasty.
5. RA patients who flare will exhibit enhanced immune activation when baseline levels are compared to levels in patients who flare within 6 weeks of surgery based on increased expression/activation of ROCK, IRF4, IRF5 and IRF8 and decreased expression/activity of their inhibitors (Def6 and SWAP-70). These molecules participate in a biologic pathway that regulates production of pro-inflammatory cytokines, potential mediators of RA flare.
6. There is a discrete set of genes expressed in circulating monocytes in RA patients during flare and prodrome of flare.

4.0 Identify and define the primary outcome and when the outcome will be measured. If measuring change in post-operative function is the most important, that will be your primary outcome.

The primary outcome is rate of RA flare within 6 weeks of surgery as measured by the OMERACT flare questionnaire.

5.0 Identify and define the secondary outcome(s) and when they will be measured (list additional goals one at a time with their corresponding outcomes).

1. The severity and impact of flares, using the OMERACT PFQs in the post arthroplasty setting: PFQs including flare intensity, duration of flare and worsening of domains associated with flare (pain, fatigue, stiffness, patient

- reported tender and swollen joint count, difficulties with coping and participation).
- 2. DAS28 at baseline and post-op week 6, and the change during this interval.

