Pending the distributions of the data, in aim 2 we will evaluate the standard mean difference or effect size for each domain (WOMAC, DAS-28, Flare questionnaire (pain, Pt global, stiffness, fatigue, coping, participation, Pt reported TJC, SJC) in patients who flare vs. those who do not based on criteria of DAS28 worsening, patient reported worsening, MD global, need to initiate or escalate treatment. We would also explore differences in long term WOMAC scores and biomarkers stratifying by flare and adjusting for unknown confounders including baseline function, age, sex, and co-morbidity score. Standard statistical tests will be used.

In aim 3 we will examine a limited number of predictors of flare within 6 weeks using appropriate statistical methods by using a generalized estimating equation and will adjust for unrecognized confounders/effect modifiers including long term WOMAC scores, baseline function, age, sex, and co-morbidity score, and biomarkers stratifying by flare. Standard statistical tests will be used.

In aim 4 we aim to determine how patients who flare meet physical therapy milestones including walking distance, and ADLs, in comparison to patients who do not flare. The evaluation of meeting physical therapy milestones is exploratory. Physical therapy milestones are routinely evaluated as post-op TJA measures and are done weekly. We will examine the distributions of change for each covariate recorded by physical therapy and compare changes in each domain stratified by flare vs. no-flare.

A potential analytic plan depending on distribution of the final data to assess PT milestones will include:

Physical therapy milestones will be assessed based on the questionnaire and analyzed as outlined below: patient VAS: continuous variable- ranging from 0 ~100, analyzed with T-test or regression

Change will be analyzed by

- 1- ANCOVA and study of change
- 2- GEE and treat delta as our continuous outcome

Walking distance: Ordinal variable - Chi-square, fisher exact

Stairs/Transfers/Activities/Driving/Employed: Nominal- Chi-square, fisher exact

We will also explore whether or not the meeting of PT milestones impacts pain and function at 1 year using the HOOS/KOOS. We will treat PT milestones as a binary and WOMAC outcomes will be analyzed as predictors.

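### Aim 2 tests DAS-28 against groups formed partly by DAS28 worsening, and Hypothesis 2 tests the PFQ against a definition containing the PFQ patient global item

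*Combined protocol and SAP*

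**What the plan says.** The documents describe the Aim 2 comparison in three places.

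- **Specific Aims, item 2.** The aim is the responsiveness of the PFQ in patients who flare, "defined as a worsening of DAS-28 by 1.2 or by 0.6 if the DAS28 was ≥ 3.2 OR by patient reported worsening". No PFQ item is named. The patient-reported part is defined under Aim 1 as "noting they are worse or much worse on the question rating their RA since pre-surgery".
- **Hypotheses, item 2.** "The OMERACT preliminary flare questions (PFQs) will detect patients who flare as defined above". The definition above it, in Hypothesis 1, requires DAS28 worsening or a worse rating, and at least one of treatment need, a rise in MD global or a rise in patient global. For patient global it refers back to the aims, where Aim 1 criterion c.iii reads "increase in patient global of 2/10 (on the OMERACT Preliminary Flare Questions [PFQ". Aim 1 also has a criterion c.iv, a flare severity score of at least 10, which Hypothesis 1 omits.
- **Sample Size and Data Analysis, item 3.0, Aim 2.** "we will evaluate the standard mean difference or effect size for each domain", where the domains are "WOMAC, DAS-28, Flare questionnaire (pain, Pt global, stiffness, fatigue, coping, participation, Pt reported TJC, SJC". Patients are split "based on criteria of DAS28 worsening, patient reported worsening, MD global, need to initiate or escalate treatment", with no AND/OR rule and no statement whether the SMD is on change or on level.

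The same Data Analysis item calls all secondary outcomes exploratory. The Background section (item 3.0) says the study will validate a tool to identify flare.

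**The concern.** A responsiveness statistic shows something only if the groups are formed without the measure being judged. If patients are sorted on DAS28 change, the sorted groups differ in DAS28 change whether or not anything happened to them. The same holds, more weakly, for patient global when it helps to admit patients to the flare group.

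At stake is the validation claim. A reader of the Aim 2 table would see a moderate or large effect size for DAS-28 beside those for the PFQ domains, and could take it as evidence of responsiveness or as the benchmark for the PFQ. Under Hypothesis 2, part of the apparent detection of flare by the PFQ would come from the PFQ's own item.

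**Working it through.** **Plan's own figure.** The documents give no effect size, SD or sample size for Aim 2. The nearest figure is the primary-aim exact test (P0 = 0.26, P1 = 0.10, N = 47). It reproduces: power 0.8143, actual alpha 0.0445. N = 47 is used below.

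**Step 1. Upper bound: one variable splits itself.** Let Z be standard normal and call the top 26% flare.
- Cut-point z = 0.6433, density φ(z) = 0.3244.
- Group means: 0.3244/0.26 = 1.2476 and −0.3244/0.74 = −0.4383; difference 1.6859.
- Within-group variances: 1 + 0.6433 × 1.2476 − 1.2476² = 0.2461, and 1 − 0.6433 × 0.4383 − 0.4383² = 0.5259.
- Pooled SD: √(0.26 × 0.2461 + 0.74 × 0.5259) = 0.673.
- SMD = 1.6859/0.673 = 2.50.

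This case applies only if DAS28 worsening alone defines flare.

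**Step 2. Noise under the written definitions.** Change scores were simulated with no true flare (500,000 patients per setting). The thresholds come from the protocol: DAS28 rise of 1.2, or 0.6 if baseline is at least 3.2; rise of 2/10 in each global. The rest are assumptions:
- baseline DAS28 mean 4, SD 1.2; DAS28 change SD 0.6 to 1.2
- SD of change in the globals 1.5 to 2.5
- 20% chance of a worse rating; 20% chance of treatment need
- error correlation r between DAS28 and patient-reported items of 0 or 0.3

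The Hypothesis 1 wording is read as (DAS28 or worse rating) and at least one supporting criterion.

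| Groups formed by | DAS-28 SMD, r = 0 | DAS-28 SMD, r = 0.3 | Patient global SMD, r = 0 | Patient global SMD, r = 0.3 |
|---|---|---|---|---|
| Aim 2 statement: DAS28 or worse rating | 0.78–1.25 | 1.15–1.61 | 0.00 | about 0.56 |
| Hypothesis 1 definition, used by Hypothesis 2 | 0.59–0.83 | 0.95–1.17 | 0.40–0.47 | 0.94–0.99 |
| Data Analysis list, any one criterion | 0.41–0.83 | 0.55–0.98 | 0.00 | about 0.3–0.4 |
| Data Analysis list, (DAS28 or worse) and (MD global or treatment)* | 0.70–0.77 | 0.88–0.95 | 0.00 | about 0.4 |
| DAS28 worsening alone | 2.2–2.4 | 2.2–2.4 | 0.00 | about 0.5 |

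*DAS28 change SD 0.9 to 1.2 only.

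PFQ domains that are not criteria have SMD 0.00 in every row at r = 0, and about 0.3 to 0.6 at r = 0.3. WOMAC is not a criterion either, so its expectation is also 0 with independent errors.

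**Step 3. At the planned size.** With N = 47, independent noise, DAS28 change SD 0.9 and global change SD 2, the chance of an observed SMD of at least 0.8 is:
- DAS-28: 79% (Aim 2 statement), 47% (Hypothesis 1 definition)
- patient global: 23% (Hypothesis 1 definition)
- other PFQ items: 1–3%

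**Step 4. Change or level.** If the SMD is taken on the week-6 level, the DAS-28 artefact is smaller but remains: 0.44 to 0.96 under the composites at r = 0, with DAS28 change SD 0.9 to 1.2.

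**The case against.** The strongest reply is that Aim 2 concerns the PFQ, and that its own statement and the Data Analysis list already keep named PFQ items out of the grouping. The plan does not set out to validate DAS-28; the Background (item 2.0) treats the DAS28 threshold as an accepted flare definition. A circular DAS-28 row does not spoil the PFQ rows. The aim is exploratory, and no power calculation depends on it.

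Most of this stands, and it limits the point. A reader might infer that large responsiveness is guaranteed from noise for the whole PFQ. The documents do not support that: pain, stiffness, fatigue, coping, participation, patient-reported joint counts and WOMAC are named as flare criteria nowhere. Nor is 0.8 certain for DAS-28 at N = 47. A reader might also take 2.5 as the size of the artefact, but every written definition is a composite, for which the figures are lower. Non-zero values for the other PFQ domains depend on a correlation that the documents do not give.

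What does not stand is the inference that nothing needs changing. DAS-28 is listed as a domain in the sentence that sorts patients on it, and Hypothesis 2 points to a definition with a PFQ item in it. The exploratory label lowers the stakes, but it does not make a circular comparison informative when the Background promises validation.

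**Conclusion.** The point holds for two comparisons: DAS-28 in the Aim 2 effect-size table, and PFQ patient global under Hypothesis 2. Neither effect size, as specified, would be evidence of responsiveness. For change scores with independent errors, the noise-only DAS-28 SMD is about 0.4 to 1.25 under the composites, rising to about 1.6 at a correlation of 0.3; 2.2 to 2.5 applies only to a DAS28-only split. For patient global under Hypothesis 2 it is about 0.4 to 0.5, or about 0.95 at a correlation of 0.3. All rest on the assumed SDs, criterion probabilities and correlations.

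Two matters remain open in the documents. They do not say whether the worse-or-much-worse question is one of the nine PFQ items, or which instrument yields the severity score. If either is part of the PFQ, the overlap is wider than shown here. The change is worth making, but it does not touch the primary analysis.

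**What to change.** 1. Reconcile the Specific Aims, the Hypotheses and the Data Analysis section to one stated Aim 2 anchor with an explicit AND/OR rule.
2. Align Hypothesis 2 with an anchor that contains no PFQ item: omit c.iii, omit c.iv if it is PFQ-derived, and confirm that the worse-or-much-worse question is not a PFQ item.
3. Do not report the DAS-28 effect size as responsiveness where DAS28 forms the groups. Report it only against a non-DAS28 anchor, such as patient-reported worsening plus treatment need.
4. State whether SMDs are on change or on level.
5. Before using MD global as an anchor, confirm that it is captured at 6 weeks. Section 2.6 implies that it is, since the staff questionnaire is repeated then, but the coordinator follow-up list in section 2.7 omits it.

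The cost is SAP wording and one or more derived variables; apart from the MD global check, the items are already planned. With independent errors, removing a measure from its own anchor returns its noise-only SMD to 0.00. The downsides are smaller apparent effect sizes and possible residual correlated reporting error (about 0.3 to 0.6 for patient-reported items at the assumed correlation of 0.3), which the report should acknowledge.

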- 3. RAPID 3 weekly for 6 weeks and every 3 months for 1 year after arthroplasty, DAS-28, HOOS, KOOS, shoulder/elbow survey, patient global at baseline, 6 weeks, and 1 year.
- 4. Physical therapy functional milestones (PT questionnaire) at baseline and weekly for 86 weeks.
- 5. Biological markers of immune activation including levels of IRF4, IRF5, IRF8, IBP/Def6, SWAP-70, ROCK1, ROCK2 in synovial tissue taken at surgery. Levels of the same immune biomarkers in the peripheral blood measured pre-operatively, at 6 weeks post-operatively and at one year post-operatively.
- 6. Measurement of discrete set of genes expressed in circulating monocytes in RA patients obtained at baseline and weekly for 6 weeks after surgery in a subset of patients at high risk for flare (based on patients who withdrew biologics)

[Help](#)

ID: 2014-233

View: 2.1 Background

[Help](#)

BACKGROUND - Be sure to answer each question individually

1.0 Explain why these research questions are being asked:

RA patients who undergo arthroplasty have severe erosive disease; preliminary data suggests a flare rate as high as 26% in the post-operative period. This study would confirm the rate of post-operative flare, and evaluate the clinical and biologic factors which predict flare. We would also look at the impact of flare on arthroplasty outcomes (HOOS, KOOS, elbow/shoulder survey) and RA disease status (HAQ, DAS-28, RAPID) and better understand the biology of flare.

Flare after arthroplasty is clinically relevant, as medications are typically withheld at the time of surgery with the aim of diminishing surgical site infections.

However, patients who flare may not be able to adhere to post-operative rehabilitation regimens, leading to worse functional outcomes. In addition, patients who flare may have difficulty achieving remission or low disease activity when medications are re-started, leading to worse disease outcomes. There is little information about the characteristics and outcome of flare in the post-operative period. Better understanding of the incidence and clinical characteristics of post-operative flare and the means to predict who will be most likely to flare could lead to more tailored management strategies and potentially better arthroplasty and disease outcomes.

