Little is known about the characteristics or rate of flare in the post-operative period, and little is known about the impact of post-operative flare on either overall disease status or arthroplasty outcome. We have shown that RA patients who undergo THR have worse outcomes at two years in WOMAC pain and function scores compared to OA controls ([name] EULAR 2013), but the reasons for this disparity are not understood. To minimize risk of infection, biologic agents are discontinued perioperatively. It is not known if increases in flare contribute to worse THR outcomes in RA patients relative to OA patients but post-operative flare needs to be considered as a likely factor. If RA patients who flare are unable to participate in postoperative rehabilitation regimens which are important in optimizing arthroplasty outcomes, they may not achieve optimal outcomes. In particular domains that worsen with flare such as fatigue and difficulty coping and participating, conceivable could contribute to a worse outcome. Paradoxically, while patients with multiple arthritic joints have worse outcomes after arthroplasty compared to patients with a singly affected joint (5), which may explain the worse outcome for RA THR patients, RA TKR patients do equally well as osteoarthritis controls, ([name] EULAR 2013). Thus factors other than polyarticular joint involvement must be impacting outcomes in RA patients undergoing THR. RA patients who have a prolonged or difficult time in re-establishing low disease activity or remission may have worse arthroplasty outcomes and this may be associated with worsening of the flare domains of joint pain and swelling, reflected by escalation to polyarticular disease (6, 7).

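### Baseline DAS28 is missing from the named covariates for 1-year outcome by flare, although the protocol expects patients who flare to start with more active RA

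*Combined protocol and SAP*

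**What the plan says.** **Expected baseline differences.** Section 2, item 3.0, Hypothesis 3 states: "RA patients who flare after TJR have worse baseline pre-operative disease activity (DAS >3.2), worse baseline function". It adds that these patients "more likely will have had a history of withdrawing a biological therapy compared to patients who do not flare". That makes three expected differences: disease activity, function and biologic withdrawal.

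**Expected outcome difference.** Hypothesis 4 says patients who flare "will have worse HOOS, KOOS, elbow, or shoulder pain and function outcomes 1 year after arthroplasty". This is worded as an association. Section 2.1, item 1.0 goes further: "We would also look at the impact of flare on arthroplasty outcomes". Section 2.1, item 3.0 speaks only of a relationship.

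**Flare definition.** Under the DAS28 criterion in Hypothesis 1, the required rise is more than 1.2 if baseline is below 3.2, and more than 0.6 if baseline is 3.2 or above.

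**Adjustment, all in Section 2.11.1, item 3.0.**
- Aim 2, long-term WOMAC scores and biomarkers by flare: "adjusting for unknown confounders including baseline function, age, sex, and co-morbidity score".
- HOOS and KOOS: logistic regression for potential confounders and effect modifiers, none of them named.
- Aim 4, physical therapy milestones: "compare changes in each domain stratified by flare vs. no-flare". The methods listed include t-test or regression, ANCOVA and GEE, with no covariates named, and chi-square or Fisher tests for the categorical milestones.
- All secondary outcomes are declared exploratory.

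**Data available.** Section 2.6 puts DAS28 in the baseline survey completed by research staff. The Coordinator Intake form in Section 2.7 records surgical joint, current biologic use, and therapies tried and stopped.

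**The concern.** Pre-operative disease activity is a candidate common cause. The protocol expects it to be higher in patients who flare, and it may plausibly also worsen the 1-year joint score. If it does both, patients who flare will score worse at 1 year even if the flare did no harm. Adjusting for baseline function removes only the part of disease activity that function carries.

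The documents intend to use the answer. Section 2.1, item 4.0 says that if patients who flare have different outcomes, it becomes important to learn how flares can be modified. A difference that reflects pre-operative severity would point to the wrong target.

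**Working it through.** **1. The plan's own figure.** The exact two-sided test of 0.26 against 0.10 with N = 47 rejects at 6 or fewer or 19 or more flares. This gives alpha 0.0445 and power 0.8143, as Section 2.11.1 states. It concerns the flare rate, not the 1-year outcome, and is used here only for group sizes:
- 47 × 0.26 = 12.2, so about 12 flarers and 35 non-flarers.
- 57 × 0.26 = 14.8, so about 15 and 42.

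**2. What the comparison can detect.** The difference detectable with 80% power at two-sided 5% is (1.960 + 0.842) × √(1/12 + 1/35) = 0.94 SD. With 15 and 42 it is 0.84 SD.

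**3. Bias formula.** All inputs here are assumptions; the documents give none.
- d: flare minus non-flare gap in baseline DAS28, in SD
- g: gap in baseline function (scored so that higher is worse), in SD
- r: within-group correlation of DAS28 with function
- β: loss in 1-year score per SD of DAS28, given function

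With a true flare effect of zero and adjustment for function only, the expected spurious flare effect is a deficit of β × (d − r × g).

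**4. Main range.** Take d = 0.5 to 0.8, β = 0.3 to 0.4 and r = 0.4. Then β × d runs from 0.3 × 0.5 = 0.15 to 0.4 × 0.8 = 0.32. The result depends on how far function also differs. False-positive rates come from simulation of a linear model, 12 against 35 patients, 4,000 runs per setting.

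| Function gap in flarers | Multiplier of β × d | Spurious deficit (SD) | False-positive rate |
|---|---|---|---|
| As large as the DAS28 gap (g = d) | 1 − 0.4 = 0.60 | 0.09 to 0.19 | 6–10% |
| Only what DAS28 carries (g = r × d) | 1 − 0.4² = 0.84 | 0.13 to 0.27 | 7–13% |
| None (g = 0) | 1 | 0.15 to 0.32 | 8–18% |

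The simulated mean deficits agree with the formula to about 0.01 SD. Hypothesis 3 expects worse function as well, so the last row is the least consistent with the protocol.

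**5. Wider range.** With d = 0.3 to 0.8, β = 0.2 to 0.4, r = 0.3 to 0.6 and g = r × d:
- lowest: 0.2 × 0.3 × (1 − 0.36) = 0.04 SD
- highest: 0.4 × 0.8 × (1 − 0.09) = 0.29 SD

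False-positive rates run from about 5%, which is no visible inflation, to about 15%.

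**6. With DAS28 added.** In every setting the mean flare estimate returns to about zero (largest 0.01 SD) and the false-positive rate to about 5%.

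**7. Scale.** Against the 0.94 SD detectable difference, the main-range bias is about one tenth (0.09/0.94) to one third (0.32/0.94).

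**The case against.** Several points on the other side stand.

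- **DAS28 is not excluded.** The aim 2 list is open-ended, and the HOOS/KOOS regression promises adjustment for unnamed confounders. Aim 3 examines baseline disease activity as a predictor of flare, so an imbalance would be noticed. However, no rule says how covariates will be chosen. With about 12 flarers, choosing them after seeing the data is what naming them in advance avoids.
- **Aim 4 is not unadjusted.** A reader might infer that the milestone comparison has no adjustment. The plan lists regression, ANCOVA and GEE; the gap is that their covariates are unnamed. Only the chi-square and Fisher comparisons cannot carry any.
- **The wording is mostly associational and the analysis exploratory.** Only the reference to impact reads causally. This limits the consequence.
- **The size is assumed and may be small.** At the weak end there is nothing to see. The simulation is linear, whereas the plan names logistic regression for HOOS and KOOS.
- **Operated joint is not shown to be a confounder.** Section 2.1, item 2.0 says "RA TKR patients do equally well as osteoarthritis controls" while RA hip patients do worse than theirs. That compares RA with OA within each joint. It does not compare RA hips with RA knees, and nothing says flare risk differs by joint. Joint matters because HOOS, KOOS and the elbow and shoulder surveys are different instruments.

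**Conclusion.** The point holds in a limited form. Baseline disease activity is a difference the protocol itself predicts, yet the one named covariate list for long-term outcome by flare omits it. An analysis that follows that list could report a flare difference that partly reflects pre-operative disease activity. The size is about 0.1 to 0.3 SD, with a false-positive rate of 6% to 18%. These figures rest wholly on the assumed gap, slope and correlation, and the lower half is more likely if function differs as much as DAS28 does.

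A reader might infer that the comparison is confounded by construction. The documents do not support that. Hypothesis 3 is a prediction, not a result. The baseline-dependent threshold makes flare status depend on DAS28, but it does not by itself settle the direction or size of any imbalance.

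Nor do the documents support a rule that Hypothesis 4 stands only if the association survives adjustment. With about 12 flarers, losing significance after adding a covariate may reflect low power, so the estimate and its interval should be read instead. The primary flare-rate analysis is unaffected.

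**What to change.** In Section 2.11.1, item 3.0:

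1. For the regression and ANCOVA comparisons of 1-year joint scores and continuous physical therapy milestones by flare status, name continuous baseline DAS28 alongside baseline function, age, sex and co-morbidity score.
2. Report the flare coefficient with its confidence interval, with and without DAS28.
3. Describe any remaining difference as an association. Acknowledge biologic withdrawal as a further expected difference and examine it in a sensitivity model if numbers allow.
4. Analyse by joint, or include joint as a term, because the instruments differ in scale; do not present it as an established confounder.

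The chi-square and Fisher milestone comparisons can remain as unadjusted description, labelled so.

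**Cost.** No new data. DAS28 takes one degree of freedom with about 12 to 15 flarers. Joint, if modelled, takes up to three more for four joint types, and analysis by joint leaves fewer patients per model, so the covariate list should stay short and be fixed in advance.
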